9.3 Other study parameters

Baseline characteristics will be summarized by means of simple descriptive statistics.

9.4 Interim analysis (if applicable)

Please also see chapter 7: safety Reporting / DSMB. The trial will be monitored by an independent DSMB. Details on the composition of the DSMB and rules on analysis and reporting are included in K5: "DSMB charter".

The trial will be stopped because of any safety issue of the treatment under study, defined as a higher occurrence of SAEs in the treatment than in the control group, any SUSAR, or any other safety concern. There will be no interim analysis for efficacy in this trial, since we consider it very unlikely that either 'futility' or 'proof beyond reasonable doubt' will be achieved prematurely in this relatively small phase 2 clinical trial.

10. ETHICAL CONSIDERATIONS

10.1 Regulation statement

The study will be conducted according to the principles of the Declaration of Helsinki (7th revision, Fortaleza, 2013) and in accordance with the Dutch Medical Research Involving Human Subjects Act (WMO) and local guidelines.

10.2 Recruitment and consent

Patients will be recruited at intensive care units at the participating hospitals. The treating intensivist / neurologist / clinical neurophysiologist will check the in- and exclusion criteria, inform a patient's legal representative, and ask for informed consent. Since any beneficial effect of the treatment under study is assumed to be larger with earlier initiation, treatment should be initiated within 12h after cardiac arrest, and as soon as possible after ICU admission. All participating centers have ample experience with inclusion of patients with acute cardiac arrest or cerebral ischemia in intervention studies. Survivors will be asked for informed consent for long term follow up (6 and 12 months) separately.

Written informed consent, documented on the informed consent form in accordance with GCP standards and study centre regulations, shall be obtained from each patient or its legal representative. First, a short version of the informed consent will be used to start the treatment within 12 hours after resuscitation. The more extensive patient information will be obtained within 48 hours after the start of trial treatment. The legal representative should sign this informed consent form as well. The original signed form will be kept in the Investigator Site File. The PI will retain a copy of the signed informed consent form in each patient's study record, and provide a copy to the patient or its legal representative.

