7. METHODS

7.1 Study parameters/endpoints

7.1.1 Main study parameter/endpoint

The primary outcome measure will be functional outcome as expressed as the score on the cerebral performance category (CPC) at 6 months.

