After randomization, daily physical, neurological, and additional examinations at the ICU will be part of routine patient care. In addition, there will be blood sampling for measurement of ghrelin concentrations at day 1 and 3, measures of neuronal damage (NSE at day 1-3), measures of cardiac damage (troponine and CK/CK-MB ratio at day 0-3), hormone concentrations (cortisol, growth hormone, prolactine, ACTH, IGF-1 at day 1-3), and highest glucose levels at day 1-7. All blood samples will be collected during routine blood sampling, if possible; preferably, there will be no additional punctures. However, blood sampling for measurement of ghrelin concentrations will be done at 30±15 minutes after treatment with ghrelin or placebo. For these measurements additional blood samples will be taken, if necessary.

Apart from the study treatment and the venous blood sampling, patients will not be subjected to additional procedures during admission.

Surviving patients will be asked informed consent for participation and additional follow-up on long term outcome. Follow up at 3 and 6 months in surviving patients will be done by telephone interview by a trained research nurse three and six months after admission. The nurse will collect CPC scores based on a standard interview. At twelve months, patients will be invited to the nearest hospital or visited at their place of residence for detailed neuropsychological examination (please see F1 testbatterij NPO for details of the test

battery). Separate informed consent will be asked for neuropsychological examination at twelve months.

Table. Overview of study procedures

	Baseline (Day 0)	Day 0-6	Day 1-7	Day 7	3m	6m	12m
Ghrelin/ placebo treatment		X					
Venous blood sampling (largely within current care)	X		X				
CPC scores				X	X	X	
Neuropsychological examination							X

M = months, CPC = Cerebral Performance Category, to be collected by a telephone interview

The total burden in hours for the patient is max 12 hours. This includes multiple transfusions of the study drug, venous blood sampling, and the follow-up procedures at 3, 6 and 12 months.

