8.2.4 Deaths

For SAEs with the outcome of death, the date and cause of death will be recorded on the appropriate case report form. Deaths that occur during the protocol that are more likely related to disease progression will be considered as an expected AE.

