9. STATISTICAL ANALYSIS

9.1 Primary study parameter(s)

The primary analysis will be a single comparison between the treatment groups of the primary outcome measure after six months. This analysis will be performed according to the intention-to-treat principle. To assess the effect of treatment with ghrelin, the whole range of the CPC will be taken into account. This indicates that no dichotomy will be used in the primary analysis. Instead of a dichotomy, any shift in the direction of a better

outcome on de CPC scale will be analyzed. This will be expressed as a common odds ratio for improvement.²⁷

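### The 6-month CPC, the primary endpoint, sits under a separate consent asked of survivors, and the protocol gives no route to it when a survivor declines or does not answer

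*Protocol*

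**What the plan says.** Protocol section 7.1.1 fixes the endpoint: "The primary outcome measure will be functional outcome as expressed as the score on the cerebral performance category (CPC) at 6 months". Section 9.1 analyses the whole scale: "This analysis will be performed according to the intention-to-treat principle", and "This will be expressed as a common odds ratio for improvement".

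Consent comes in stages. Under section 10.2 a short form is signed so that treatment can start, and the fuller information follows within 48 hours of the start of treatment, with the legal representative signing again. The same section then adds: "Survivors will be asked for informed consent for long term follow up (6 and 12 months) separately". It names 6 and 12 months and is silent on 3 months.

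Section 7.3 has its own survivor consent: "Surviving patients will be asked informed consent for participation and additional follow-up on long term outcome". It continues: "Follow up at 3 and 6 months in surviving patients will be done by telephone interview by a trained research nurse". A further step is kept for the last visit: "Separate informed consent will be asked for neuropsychological examination at twelve months".

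Deaths follow another path. Section 8.2.4 says: "For SAEs with the outcome of death, the date and cause of death will be recorded on the appropriate case report form".

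Two other rules bear on this. Section 7.6 promises an effort to complete the primary follow-up, but under a heading about withdrawal from treatment. Section 7.5 replaces subjects who withdraw, whatever the reason.

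**The concern.** A patient who dies during the trial gets an outcome from the SAE record. A patient who survives gets one from a telephone interview that, read literally, needs a second consent. If that consent is declined or never returned, the protocol does not say whether or how the 6-month CPC may still be recorded. By this route the chance of a missing primary outcome depends on the outcome itself.

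Three things are at stake:

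- **Precision.** The sample size carries no margin for lost outcomes.
- **Bias.** If survivors are lost at different rates in the two arms, or if loss depends on CPC level, a comparison of observed outcomes is distorted.
- **The analysis set.** If a declining survivor is counted as withdrawn, section 7.5 would replace that patient, which sits badly with intention to treat.

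The two consent passages are also hard to apply together. Section 10.2 groups the 6-month primary endpoint with the 12-month follow-up. Section 7.3 asks for one consent to participation and follow-up and a further one for the 12-month examination alone. A site cannot tell which form governs the 6-month call.

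**Working it through.** **Inputs from the protocol.** N = 160, control mean CPC 3.20, SD 1.8, difference 0.8, alpha 0.05, power 80% (section 4.4); 1:1 allocation (section 7.2); expected case fatality 50-60% (section 8.2.1).

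**Assumptions.** The share r of survivors who decline or do not answer is not in the protocol; 5%, 10% and 20% are used. CPC 5 is taken to be death. The protocol does not define the levels, but section 8.5 notes that safety endpoints and the primary endpoint overlap.

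**Step 1: the plan's own figure.** With a two-sided test, n per arm = 2 × [1.8 × (1.960 + 0.842) / 0.8]² = 79.5, so 80 per arm and 160 in total. Power at 80 per arm is 80.3%. The 160 reproduces with no addition for missing outcomes.

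**Step 2: share of survivors.** Case fatality of 50-60% leaves 40-50% alive. One illustrative distribution that matches section 4.4 is CPC 1-5 = 29/19/3/1/48%:

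- mean = 0.29 + 0.38 + 0.09 + 0.04 + 2.40 = 3.20
- variance = 13.48 − 3.20² = 3.24, so SD = 1.80

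It leaves 52% alive. The range used is therefore 40-52%.

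**Step 3: lost outcomes and power.** Lost = 160 × survivor share × r. Power is recomputed with the remaining N split equally, at the planned 0.8 and 1.8.

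| r | Lost, 40% alive | Lost, 50% alive | Lost, 52% alive | Power |
|---|---|---|---|---|
| 5% | 3.2 | 4.0 | 4.2 | about 79% |
| 10% | 6.4 | 8.0 | 8.3 | 78-79% |
| 20% | 12.8 | 16.0 | 16.6 | 76-77% |

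**Step 4: equal loss in both arms.** Observed survival is s(1 − r) / [s(1 − r) + (1 − s)]. With s = 0.52 it falls from 52% to 50.7%, 49.4% or 46.4%. The survival odds in each arm are multiplied by the same (1 − r), so their ratio is unchanged. To check the mean difference, take a control distribution of 33/13/3/1/50% (mean 3.22, SD 1.85) and a treated arm shifted by a common odds ratio of 2.30, which gives a true difference of 0.80. With 20% loss in both arms the observed difference is 0.82. With a higher-fatality control distribution (28/10/1/1/60%) it is 0.79. With no drug effect there is no bias.

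**Step 5: unequal loss, no drug effect, 29/19/3/1/48% in both arms.** Survivors contribute 0.80 to the mean and deaths 2.40.

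- r = 5%: (0.80 × 0.95 + 2.40) / (0.52 × 0.95 + 0.48) = 3.160 / 0.974 = 3.244
- r = 15%: (0.80 × 0.85 + 2.40) / (0.52 × 0.85 + 0.48) = 3.080 / 0.922 = 3.341
- spurious difference: 0.096 CPC points
- survival odds ratio factor: 0.95 / 0.85 = 1.12, or 0.89 the other way round

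With 10% against 30% loss and the 33/13/3/1/50% distribution, the spurious difference is about 0.22.

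**The case against.** The other side has several good arguments, and they limit the point without removing it.

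**Sections 7.3 and 10.2 may not conflict.** A reader might infer that 7.3 treats the 6-month call as ordinary follow-up and asks separate consent only for the 12-month examination. The text does not support that. Section 7.3 also asks survivors for consent to participation and long-term follow-up, just before it describes the 3- and 6-month calls. The survivor consent is in both places, and amending 10.2 alone would leave it standing in 7.3.

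**A bar on collection is inferred.** The protocol does not state what the representative's forms cover after the acute phase, and the consent pages are not available for review. That a site may not record the CPC without the survivor's form is a plausible reading, not a stated rule.

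**Losses are not strictly confined to survivors.** A reader might also infer that every missing outcome belongs to a survivor and that every death is known. Neither follows. Section 7.4 lets anyone leave at any time, and the full form can come up to 48 hours after treatment starts, so a representative could withdraw a patient who later dies. A survivor who declines follow-up could die before 6 months, and no check of vital status is described.

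**Survivors may refuse under any wording.** Asking patients who regain capacity is proper, so part of the loss is unavoidable, and the share due to this wording cannot be estimated from the document.

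**Bias is conditional.** The trial is double blind and nothing in the protocol suggests that refusal would differ by arm. The factor of 1.12 applies to the survival odds ratio, not to the common odds ratio of the primary analysis. A shift of 0.10 is one eighth of the planned 0.8.

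What remains is that 10.2 names the primary time point as subject to a separate survivor consent, and no fallback is given.

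**Conclusion.** The point holds in a limited form. As written, the protocol makes collection of the primary outcome depend on a consent asked of survivors and leaves no route to the 6-month CPC if that consent is not given. Missingness by this route depends on the outcome, and the 160 has no reserve for it.

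The likely size is modest: on the assumed loss of 5-20% of survivors, 3 to 17 outcomes and one to four points of power. The documents do not support saying that the treatment comparison will be biased. That needs loss that differs by arm or by CPC level. The 5% against 15% case shows what such a gap would do, not what is expected. How missing CPC values are analysed may be set out in the SAP and is not part of this point.

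This should be fixed because the remedy is cheap and a primary outcome that was never collected may not be recoverable later. It does not undermine the design.

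**What to change.** Amend sections 10.2 and 7.3 together:

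- State that the 3- and 6-month CPC is part of the main consent, meaning the representative's full form and the survivor's consent to continued participation.
- Restrict the separate consent to the 12-month neuropsychological examination.
- For survivors who decline further contact, ask specifically for permission to record the 6-month CPC, or at least vital status, from a proxy, the general practitioner or hospital records.
- State that a survivor who declines stays in the intention-to-treat population and is not replaced under section 7.5.

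The cost is a protocol amendment and revised consent forms with ethics review. No extra visits or staff are needed. Survivors keep the right to object, so some loss will remain.

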10.3 Benefits and risks assessment, group relatedness

This study is conducted in comatose patients after cardiac arrest. This group of patients is by definition (at least temporarily) incapacitated.

Severe postanoxic encephalopathy after cardiac arrest is one of the most common causes of coma worldwide. In the Netherlands alone, 3000-5000 patients are admitted, yearly. Half of all patients never awaken and die as a result of severe postanoxic encephalopathy. In the other half, there is a large probability of lasting brain damage with functional and cognitive impairments. Impact on patients and their families is huge. Specific treatments to improve brain recovery are unavailable and urgently needed. Over

the past years, there has been no substantial scientific progress. The only general treatment of presumed benefit is cooling the brain to 32°C, although its gain has become uncertain since the recent Targeted Temperature Management trial, and mechanisms of action are unclear.³ Any new effective treatment to improve cerebral recovery and functional outcome will be of large relevance for patients, families, and society given the high incidence and large impact of the disease, and the large probability of a poor outcome without treatment.

Ghrelin is a naturally occurring 28 amino acid peptide functioning as a hormone (stimulating secretion of growth hormone) and mildly excitatory neurotransmitter. It is mainly produced in the stomach. The bioactive form, acylated ghrelin, represents 10% of the total amount of circulating ghrelin. A primary function is signaling nutrient availability from the gastrointestinal tract to the brain. Ghrelin is present in the healthy brain, where it influences mood, sleep-wake rhythm, learning, memory, and neurogenesis.¹⁸ Ghrelin has been tested in over one hundred human studies, including healthy volunteers, patients with (severe) cardiopulmonary diseases, and neurodegenerative diseases. Serious adverse events were extremely rare and difficult to attribute to ghrelin.¹⁷

In an *in vitro* model of postanoxic encephalopathy, treatment with Ghrelin restored activity levels and had a large beneficial effect on neuronal survival and synapse formation.⁹ In a state of the art rat model of cardiac arrest, ghrelin treatment attenuated histologically proven hypoxic brain injury, and improved functional recovery.¹⁰ In another established model of global forebrain ischemia, ghrelin treatment improved neuronal survival as tested immunocytochemically.¹⁵ In over ten rat studies on focal cerebral ischemia and reperfusion (mainly by intraluminal vessel occlusion), ghrelin improved neuronal survival and functional recovery without exception, where in most studies it was assumed that ghrelin prevented apoptosis.¹²⁻¹⁵

We propose to measure the effect of ghrelin on neurological recovery of comatose patients after cardiac arrest based on the large probability of a poor outcome in this patient group, lack of effective treatments to promote brain recovery, consistent beneficial effects of ghrelin under experimental *in vitro* and *in vivo* conditions, and substantial evidence of safety.

10.4 Compensation for injury

The Principle Investigator has a liability insurance which is in accordance with article 7 of the WMO.

The Principle Investigator (also) has an insurance which is in accordance with the legal requirements in the Netherlands (Article 7 WMO). This insurance provides cover for damage to research subjects through injury or death caused by the study. The insurance applies to the damage that becomes apparent during the study or within four years after the end of the study.

11. ADMINISTRATIVE ASPECTS, MONITORING AND PUBLICATION

11.1 Handling and storage of data and documents

For data collection and management, the Research Manager software will be used. All sites will receive a unique code and all patients will receive a study number by which all data will be coded. The principal investigator or trained and delegated member of the research team will have access to the coded source data, if necessary.

Several variables will be collected from hospital records for the purpose of this study as described in paragraph 6.3. The data required for the trial will be entered by the investigation sites into eCRFs in Research Manager. All site staff will be trained on correct eCRF completion. Only trained personnel will receive access and be able to enter data in the eCRF. The eCRF will not be considered as source data.

Study related correspondence, patient records, signed Informed Consent Forms and source documents are to be maintained by the study site for a minimum of 15 years after the end of this trial.

A patient code will consist of two parts. The first part refers to the hospital, the second part to the patient. The second part of the code starts with 001, 002, 003 ... in each center.

Coded data will be stored in Research Manager, which is fully validated and has an audit trail. Access to the data will only be provided to the researchers that are involved in the study. They will be delegated by the local PI by a delegation log. Research Manager distinguishes specific roles, for example, PI, nurse, pharmacist, monitor, DSMB. Data will be stored for 15 years.

Research Manager has a daily full back up to a dedicated backup server on a secure location (14 days storage). The backups are encrypted (AES 256).

Research Manager has a daily full back up to an external backup location on a secure location. The backups are encrypted (AES 256).

Research Manager has a weekly full back up to a dedicated backup server on a secure location. The backups are encrypted (AES 256).

Research Manager backup restore is tested periodically.

11.2 Monitoring and Quality Assurance

A site initiation visit will be performed after it has been verified that the site is prepared for the study and that the site requirements for study participation are met. During this training the study personnel will get all the information needed about the protocol, study procedures and the online database (Research Manager).

In accordance with Good Clinical Practice (GCP) guidelines, there will be a monitor system. Herewith it will be verified that

- (a) the rights and well-being of the included patients are protected
- (b) reported trial data are accurate, complete, and verifiable from source documents.
- (c) the conduct of the trial is in compliance with the currently approved protocol, with GCP, and with applicable regulatory requirements.

Monitoring will be done by trained personnel and with adequate frequency to ensure that the investigator's obligations are being fulfilled. Frequency and timing of monitoring visits shall be determined by the Principle Investigator for each site based on enrolment rate and volume, study compliance and findings from previous visits. Details are described in the monitoring plan.

It will be verified whether signed and dated informed consent forms have been obtained from each subject before any study related procedures are undertaken. Also, compliance with the study protocol will be checked..

11.3 Annual progress report

The Principle Investigator will submit a summary of the progress of the trial to the accredited METC once a year. Information will be provided on the date of inclusion of the first subject, numbers of subjects included and numbers of subjects that have completed the trial, serious adverse events/ serious adverse reactions, other problems, and amendments.

11.4 Public disclosure and publication policy

This trial will be publicly registered in accordance with the Declaration of Helsinki on www.trialregister.nl.

Publications will be by the executive committee, in the name of the steering committee. Pre-defined sub-studies or post-hoc analysis by participating investigators are possible after consultation of the executive committee and only after publication of the primary results of the trial.

The executive committee consists of [name], [name], [name], [name], and [name] and the study-coordinator (PhD student at the University of Twente). The steering committee consists of one or two additional local investigators from each participating center, and the executive committee. The steering committee will make decisions regarding continuation of the trial and protocol changes. Decisions will be prepared by the executive committee. The chairman of the steering committee (i.e. the principal investigator) will be advised by the independent data monitoring and safety committee. The study-coordinator is responsible for running the trial on a day-to-day basis, and will report to the executive committee.

12. STRUCTURED RISK ANALYSIS

12.1 Potential issues of concern

a. Level of knowledge about mechanism of action

Ghrelin is a naturally occurring 28 amino acid peptide functioning as a hormone (stimulating segregation of growth hormone) and mildly excitatory neurotransmitter. It is mainly produced in the stomach. The bioactive form, acylated ghrelin, represents 10% of the total amount of circulating ghrelin. A primary function is signaling nutrient availability from the gastrointestinal tract to the brain. Ghrelin is present in the healthy brain, where it influences mood, sleep-wake rhythm, learning, memory, and neurogenesis.¹⁸

Treatment with Ghrelin consistently improved functional recovery after cerebral ischemia in various living animal models.^{10,12-14} Hereby, better functional recovery was associated with prevention of neuronal apoptosis. In an *in vitro* model of postanoxic encephalopathy, ghrelin prevented neuronal death by improved synapse recovery.⁹ Taken together, it is assumed that the beneficial effects of ghrelin with regard to recovery of brain functioning after cardiac arrest are mediated by mild neuronal activation, preventing ill-fated neuronal inactivity, and thus preventing apoptosis.⁵ This is perpendicular to the classical view of neuroprotection by inhibition.

b. Previous exposure of human beings with the test product(s) and/or products with a similar biological mechanism

Ghrelin has been administered as an infusion or a bolus in a variety of doses to at least 1850 study participants, including healthy participants and patients with obesity, prior gastrectomy, cancer, pituitary disease, diabetes mellitus, eating disorders, cardiovascular disease and neurodegenerative disease.^{17,18} There is strong evidence that ghrelin stimulates appetite and increases circulating GH, ACTH, cortisol, prolactin, and glucose across varied patient populations. There is a paucity of evidence regarding the effects of ghrelin on LH, FSH, TSH, insulin, lipolysis, body composition, cardiac function, pulmonary function, the vasculature, and sleep. Adverse effects occurred in 20% of participants, with a predominance of flushing and gastric rumbles and a mild degree of severity. The few serious adverse events occurred in patients with advanced illness and were not clearly attributable to ghrelin.¹⁷

c. Can the primary or secondary mechanism be induced in animals and/or in ex-vivo human cell material?

Acyl ghrelin passes the blood-brain barrier after intravenous application.²⁸ Studies in a variety of animal models of neuronal injury have demonstrated neuroprotective effects.²⁹ In rat models of traumatic brain injury, ghrelin treatment increased survival and facilitated function recovery by suppressing inflammation and apoptosis.^{30,31} In models of transient cerebral ischemia, ghrelin decreased infarct volumes and significantly reduced the expression of active cleavage products and apoptosis.¹²⁻¹⁴ After global forebrain ischemia, ghrelin treatment was associated with less severe damage of hippocampal CA1 neurons.¹⁵ In a state of the art model of coma after cardiac arrest, ghrelin treatment improved functional recovery and was associated with less apoptosis and less severe neuronal damage on histological examination.¹⁰

d. Selectivity of the mechanism to target tissue in animals and/or human beings

Although des-octanoyl (unacylated) ghrelin is found in higher serum concentrations, acylated ghrelin is the active form, responsible for effects in the brain. There are two variants of the central ghrelin receptor: GHS-R1a and GHS-R1b. The first has features of a typical G protein coupled receptor. The latter has been reported as an inactive form without signaling activity.³² Following the discovery of ghrelin, various studies have demonstrated its importance in regulating food intake and body weight. These effects are largely driven by a high expression of GHS-R1a in the hypothalamus and pituitary. However, GHS-R1a is also expressed in the hippocampus, cortex, thalamus, raphe nuclei, ventral tegmental area, and substantia nigra,³³ mediating multiple physiological functions beyond those involved in metabolic activity. For example, ghrelin was able to regulate learning and memory, reward-seeking behavior, anxiety, and depression,^{34,35} and had neuroprotective effects in neurodegenerative diseases.³⁶⁻³⁹

e. Analysis of potential effect

At the doses evaluated in the 66 published studies with adverse event reporting, ghrelin demonstrated an excellent short-term safety profile with few adverse effects.¹⁷ Serious adverse events such as pneumonia, enteritis, and lung cancer were extremely rare and difficult to attribute biologically to ghrelin administration. Most of the severe adverse events derived from 1 study of ghrelin v.s placebo administration in severely ill patients with pulmonary cachexia, a group that is vulnerable to developing additional medical problems.¹⁹ Mild adverse events occurred in approximately 20% of participants receiving ghrelin. The most common effect was transient flushing, which occurred in 10% of volunteers, but resulted in discontinuation of study medication in only 3 of the 939 participants in whom

adverse event collection was reported.²⁰⁻²² There was no difference in the percentage of participants experiencing flushing between bolus and infusion routes of administration. Larger ghrelin doses may increase the risk of flushing, as indicated by the higher rate of flushing in the 2 ghrelin bolus studies that employed the largest tested dose (10µg/kg). The most common gastrointestinal side effect was gastric rumbles, which occurred in 22 participants (2.3%) and was never severe enough to lead to ghrelin discontinuation. Gastrointestinal side effects and increased thirst were more common in volunteers who received continuous ghrelin infusions, perhaps due to the longer duration of exposure to ghrelin. Few participants developed neurocognitive effects including somnolence, fatigue, vertigo, or change in mood (26 subjects, 2.8%). These effects were more common in subjects who received ghrelin bolus, potentially due to the rapid ghrelin delivery.¹⁷ To minimize risks, we chose to apply short term infusion in at least 30 minutes, rather than bolus infusion in a narrower sense.

f. Pharmacokinetic considerations

Intravenously administered ghrelin is rapidly cleared. Fifteen minutes after administration of a single 1 or 5µg/kg bolus, total ghrelin plasma concentrations rose to 1059 and 6599fmol/l, from a mean baseline level of 169. Elimination half-life was 27 to 31 minutes.³⁶ A 61-fold increase in circulating total ghrelin has been reported 1 minute after iv injection of 10µg/kg with an elimination half-life of 10 minutes.

g. Study population

Our study population consists of freshly resuscitated patients after cardiac arrest. These patients suffer from a life threatening disease and may be hemodynamically unstable. All patients are admitted to an intensive care unit. Our study population may be exceptionally vulnerable to cardiovascular adverse events.

In previous studies, cardiovascular effects of ghrelin were beneficial rather than detrimental. In healthy men, low-dose ghrelin infusion was associated with increased mean peak myocardial systolic velocity.⁴⁰ A large ghrelin iv bolus increased stroke volume and decreased systemic vascular resistance and mean arterial pressure (MAP) in healthy volunteers,⁴¹ although a similar dose of sc ghrelin increased LVEF without change in MAP.⁴² In participants with heart failure, higher and repeat dose infusions decreased MAP, pulmonary capillary wedge pressure, and systemic vascular resistance and increased cardiac index, stroke volume, and LVEF; these changes were associated with improved exercise capacity.^{43,44} In these previous studies, cardiac effects of ghrelin were dose and route dependent, with greater potency from iv ghrelin compared to the sc route.

h. Interaction with other products

We know of no relevant pharmacokinetic or pharmacodynamics interactions between ghrelin and standard treatment modalities for patients after cardiac arrest.

i. Predictability of effect

There are no known biomarkers for effect of ghrelin on neurological or cardiovascular outcomes.

j. Can effects be managed?

There are no antidotes or antagonists available. Since all patients are initially admitted on intensive care units, access to adequate medical support is guaranteed.

